#### LIST OF ABBREVIATIONS AND RELEVANT DEFINITIONS

ABR	ABR form, General Assessment and Registration form, is the application form that is required for submission to the accredited Ethics Committee (In Dutch, ABR = Algemene Beoordeling en Registratie)
AE	Adverse Event
AR	Adverse Reaction
CA	Competent Authority
CCMO	Central Committee on Research Involving Human Subjects; in Dutch: Centrale Commissie Mensgebonden Onderzoek
DSMB	Data Safety Monitoring Board
EudraCT	European drug regulatory affairs Clinical Trials
GCP	Good Clinical Practice
IB	Investigator's Brochure
IC	Informed Consent
IMP	Investigational Medicinal Product
IMPD	Investigational Medicinal Product Dossier
METc	Medical research ethics committee (MREC); in Dutch: Medisch Ethische Toetsing Commissie (METc)
(S)AE	(Serious) Adverse Event
SPC	Summary of Product Characteristics (in Dutch: officiële productinformatie IB1-tekst)
Sponsor	The sponsor is the party that commissions the organisation or performance of the research, for example a pharmaceutical company, academic hospital, scientific organisation or investigator. A party that provides funding for a study but does not commission it is not regarded as the sponsor, but referred to as a subsidising party.
SUSAR	Suspected Unexpected Serious Adverse Reaction
Wbp	Personal Data Protection Act (in Dutch: Wet Bescherming Persoonsgegevens)
WMO	Medical Research Involving Human Subjects Act (in Dutch: Wet Medisch-wetenschappelijk Onderzoek met mensen)
IBD	Inflammatory Bowel Disease
F. prausnitzii	Faecalibacterium prausnitzii
M. Crohn	Morbus Crohn
E. coli	Escherichia coli
FISH	fluorescent in situ hybridization
UMCG	University Medical Center Groningen
SCFAs	Short Chain Fatty Acids

## The effect of riboflavin supplementation on *Faecalibacterium prausnitzii* in Crohn's disease

### SUMMARY

#### Rationale

Recent studies show that in patients with Inflammatory Bowel Disease (IBD) a dysbiosis exists in the composition of the intestinal microbiota. In particular, the potentially pathogenic bacterium *Escherichia coli* (*E. coli*) is often more abundant in the bowel of IBD patients, and the anaerobic commensal *Faecalibacterium prausnitzii* (*F. prausnitzii*) is often reduced. This last mentioned bacteria is known to be abundant in the intestine of healthy individuals. It is known to produce butyrate, which stimulates the intestinal epithelium, and to secrete anti-inflammatory substances.

Riboflavin – also known as vitamin B2 – is required for a wide variety of cellular processes and has an important role in maintaining health in humans. In a pilot intervention with healthy volunteers it is shown that a riboflavin supplement increases the number of *F. prausnitzii* and results in a higher production of butyrate. In Crohn's disease patients, it is known that the amount of *F. prausnitzii* in the intestine is generally low. Furthermore, it is known that there is an association between the number of *F. prausnitzii* bacteria and the length of disease in remission.

This study will evaluate if supplementation of the diet with riboflavin in Crohn's disease patients will result in a similar increase in the amount of *F. prausnitzii* as in healthy volunteers. In this patient group, an increase in the number of *F. prausnitzii* bacteria in the bowel may result in a more favourable disease course. This will be assessed with faeces calprotectin and two questionnaires. Additionally we will assess if there is any modulation by riboflavin on the other intestinal bacteria, short chain fatty acids (SCFAs) (such as butyrate), and the pH of the faeces. Finally, the effect of the riboflavin on the permeability of the gut will be evaluated with a Chromium-EDTA test, and a number of different biomarkers of permeability.

#### Hypothesis

The hypothesis is that in Crohn's disease patients, supplementation of the diet with riboflavin results in an increase in the amount of *F. prausnitzii*, changes in microbial composition, increased fatty acid production, an increase in pH and a reduction of intestinal permeability. These changes might result in a more favourable disease course with less exacerbations.

#### Study design

Prospective clinical study.

#### Study population and sample size

In total 84 Crohn's disease patients will be included in this study, divided into two groups. Group 1 (n=42) will consist of patients with disease in remission (quiescent disease); group 2 (n=42) will consist of patients with active disease. In this study an adaptive design will be

### The effect of riboflavin supplementation on *Faecalibacterium prausnitzii* in Crohn's disease

used. First 12 patients in the disease in remission group will be analysed. The methods of analysis and safety aspects will be taken into account.

#### Intervention

Supplementation of the normal diet with 1 capsule of 100 mg riboflavin (vitamin B2) during three weeks.

#### Main study parameters

##### Primary Objective:

1). To investigate the effect of a riboflavin supplement on the number of *F. prausnitzii* bacteria in the faeces of active and quiescent Crohn's disease patients.

##### Secondary Objectives:

1). To evaluate the effect of a riboflavin supplement on the bacterial composition in the faeces of active and quiescent Crohn's disease patients.

2). To evaluate the effect of a riboflavin supplement on the production of short chain fatty acids (SCFAs) in the faeces of active and quiescent Crohn's disease patients.

3). To assess the effect of the riboflavin intervention on the disease severity (Harvey Bradshaw Index, IBD-Q and faeces Calprotectin) of active and quiescent Crohn's disease patients.

4). To evaluate the effect of the riboflavin intervention on permeability of the gut in active and quiescent Crohn's disease patients (Chroom-EDTA test, and different biomarkers of permeability).

5). To determine the effect of a riboflavin supplement on the faecal pH in active and quiescent Crohn's disease patients.

6). To evaluate whether riboflavin intervention leads to an increase in electrical current in the faeces, as a result of an increase in extracellular electron shuttling bacteria.

#### Nature and extent of the burden and the risks associated with participation, benefit and group relatedness

Participating in this study has a potential health benefit. It is known that in healthy subjects, the supplement riboflavin increases the amount of beneficial bacteria. In Crohn's disease there is often a dysbiosis of the bacterial composition, and the beneficial bacteria are depleted. When a similar increase in the beneficial bacteria occurs in Crohn's disease patients as seen in healthy volunteers, this may result in a more favourable disease outcome (staying in remission longer). Riboflavin is freely available, and commonly sold in health shops. There is no need for a prescription to buy this supplement, and its use is considered to be safe. The riboflavin supplement may give a (completely innocent) yellow discoloration of the urine several hours after ingestion. There is no need to discontinue the riboflavin supplementation. The adverse event of discoloration of urine is only temporary.

## The effect of riboflavin supplementation on *Faecalibacterium prausnitzii* in Crohn's disease

### 1. INTRODUCTION AND RATIONALE

#### Rationale

##### Bacterial dysbiosis in IBD

The most common types of Inflammatory Bowel disease (IBD) are M. Crohn and Ulcerative Colitis (UC). Although there are many differences between these diseases, both are characterized by an altered composition of the gut microbiome. (1)

Microbiota generally play an important physiological role in the digestion of nutrients. However, in patients with a particular genetic predisposition it has been suggested that an aberrant immune response against the intestinal microbiota takes place. (2) (3) We have previously shown that specific bacteria are essential in developing an experimental colitis (model of an experimental colitis). (4) In Crohn's disease it appears that pro-inflammatory and anti-inflammatory microbiota are out of balance. Recently we showed that this imbalance is also responsible for developing a humoral immune response against the own gut bacteria as is demonstrated by IgG coating of bacteria. (5) From a clinical practice it has long been known that an elemental diet can achieve remission of disease activity. (6) The exact mechanism that underlies this finding is yet to be discovered. We believe that this elemental diet changes the bacterial composition in the intestine and restores the dysbiosis.

The dysbiosis as seen in IBD is characterized by an increase in the number of potentially pathogenic bacterium *Escherichia coli* (*E. coli*) and a reduction of the anaerobic gram-positive commensals in the intestine (such as bacteria belonging to the *Clostridium* groups IV en XIVa). (7) (5) (8) (9) (10) These *Clostridium* groups are bacteria that convert complex carbohydrates and sugars into fatty acids such as butyrate. One of the bacteria of the *Clostridium* group IV (and the phylum of Firmicutes) is *Faecalibacterium prausnitzii* (*F. prausnitzii*), a bacterium that generally forms around 10% of our gut microbiota and occurs in almost every human being. (11)

*F. prausnitzii* can grow on sugars, pectin and degradation products of human mucus. From glucose and acetate it produces in particular butyrate, which stimulates the intestinal epithelium by influencing regeneration and gene expression, stimulating mucus production and by reducing the permeability of the gut. (12) Butyrate is also the main source of energy for the colonocytes in the intestine. Butyrate belongs to the group of short chain fatty acids (SCFAs). SCFAs are produced as a product of microbial fermentation of indigestible carbohydrates. (13) (14) (15) Moreover, *F. prausnitzii* produces soluble substances which have an anti-inflammatory effect on the immune system of the intestine. (7) Furthermore, in mice it is shown that oral administration of live *F. prausnitzii* or its supernatant markedly reduced the severity of TNBS colitis (murine model for colitis) and tended to correct the

### The effect of riboflavin supplementation on *Faecalibacterium prausnitzii* in Crohn's disease

dysbiosis associated with TNBS colitis models. (7) Although it is difficult to cultivate *F. prausnitzii*, due to its extreme sensitivity to oxygen, it was recently demonstrated that a culture medium of riboflavin and cysteine makes growth of this bacteria at low oxygen levels possible. (16)

Riboflavin – also known as vitamin B2 – is required for a wide variety of cellular processes, and has an important role in maintaining health in humans. Riboflavin enables the bacterium *F. prausnitzii* to use a form of anaerobic respiration, by use of external electron acceptors such as cysteine and oxygen. This results in the growth of *F. prausnitzii* in vitro at low oxygen levels. This may also be the case in the intestinal wall mucosa. (16) In a pilot intervention with healthy volunteers it is shown that a riboflavin supplement increases the number of *F. prausnitzii* in the faeces and results in a higher production of butyrate (results yet to be published, see Figure 1). It is shown that in Crohn's disease there is a depletion of vitamin B2 level as compared with healthy controls, and that the level of this vitamin showed a negative correlation with the Crohn's disease activity index. (17) Also, in Crohn's disease patients, it is known that the amount of *F. prausnitzii* in the intestine is generally low. There is an association between the number of *F. prausnitzii* in the bowel and the length of disease in remission. (see Figure 2).

**Figure 1: A study in healthy volunteers shows an increase in the number of *F. prausnitzii* in the faeces during riboflavin supplement intake in the majority of the subjects.**

## The effect of riboflavin supplementation on *Faecalibacterium prausnitzii* in Crohn's disease

**Figure 2: *F. prausnitzii* proportions in the ileal mucosa-associated microbiota using FISH at the time of surgery and at 6 months according to the endoscopic recurrence status. \*, Significant difference, P = 0.03. Sokol H et al. PNAS 2008;105:16731-16736.**

The present study will evaluate if supplementation of the diet with riboflavin in Crohn's disease patients will result in a similar increase in the amount of *F. prausnitzii* as seen in the healthy volunteers. Potentially an even larger effect can occur, because of the low starting amount. In this patient group, an increase in the number of *F. prausnitzii* in the bowel may result in a more favourable disease course. (7) A possible protective effect of *F. prausnitzii* in the development of IBD has been suggested in a number of studies. (8) (7) (11) (18) Our hypothesis is that supplementation of the diet with riboflavin will result in an increase in the amount of *F. prausnitzii*. We hypothesize that this will be more pronounced in the Crohn's disease patients with disease in remission, than in the group with active disease. This because, cytokines and mediators of inflammation might counteract the beneficial effect of the riboflavin on *F. prausnitzii*. Further, we hypothesize that as a result of the increase in *F. prausnitzii*, butyrate production will increase. (8) (18) (19) (20) Butyrate is thought to play a beneficial role on reducing the inflammation of the intestinal mucosa; the exact mechanism(s) are yet to be defined. (18) We expect the pH of the faeces to increase after the riboflavin intervention, since, the faeces pH is shown to be lower in inflammatory conditions, and riboflavin might result in a reduction of the inflammation. (21) Also, the permeability of the gut will be evaluated with a Chroom-EDTA test, and a number of different biomarkers of permeability. A decrease in permeability is hypothesized as a result of reduced inflammation. (7) (8) Finally Khan et al demonstrated that *F. prausnitzii* uses riboflavin for electron transfer. In this study it was shown that riboflavin is required for the extracellular shuttling of electrons by *F. prausnitzii* that metabolize glucose anaerobically. We will evaluate whether riboflavin intervention leads to an increase in electrical current, as a result of an increase in extracellular electron shuttling bacteria. (16)

Previous studies have analysed the effect of different nutritional supplements in Crohn's disease patients. In a group of patients with inactive or mild disease it was shown that a vitamin E and C supplement resulted in a significant reduction in oxidative stress. (22) In an article of Ramirez-

## The effect of riboflavin supplementation on *Faecalibacterium prausnitzii* in Crohn's disease

Farias et al 2008 it is shown that the dietary supplement inulin is able to increase the number of *F. prausnitzii* bacteria in the bowel from 10.3% during the control period to 14.5% during inulin intake (increase of 41%) (23). Until now, no study has been performed that evaluated the effect of a vitamin B2 supplement on the intestinal microbiota.

In conclusion, the present study will evaluate the effect of the vitamin supplement riboflavin on the intestinal bacterial composition in Crohn's disease patients. Dysbiosis of the intestinal microbiota is generally seen in Crohn's disease. Restoring this dysbiosis may lead to a more favourable disease course with less exacerbations.

## 2. OBJECTIVES

### Research Goals

#### Primary Objective:

1). To investigate the effect of a riboflavin supplement on the number of *F. prausnitzii* bacteria in the faeces of active and quiescent Crohn's disease patients.

#### Secondary Objectives:

- 1). To evaluate the effect of a riboflavin supplement on the bacterial composition in the faeces of active and quiescent Crohn's disease patients.
- 2). To evaluate the effect of a riboflavin supplement on the production of short chain fatty acids (SCFAs) in the faeces of active and quiescent Crohn's disease patients.
- 3). To assess the effect of the riboflavin intervention on the disease severity (Harvey Bradshaw Index, IBD-Q and faeces Calprotectin) of active and quiescent Crohn's disease patients.
- 4). To evaluate the effect of the riboflavin intervention on permeability of the gut in active and quiescent Crohn's disease patients (Chroom-EDTA test, and different biomarkers of permeability).
- 5). To determine the effect of a riboflavin supplement on the faecal pH in active and quiescent Crohn's disease patients.
- 6). To evaluate whether riboflavin intervention leads to an increase in electrical current in the faeces, as a result of an increase in extracellular electron shuttling bacteria.

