### Riboflavin intervention

The study is designed in such a way that the participants are their own controls (control period). After signing the informed consent patients are asked to collect a stool sample to measure the amount of *Faecalibacterium prausnitzii* (*F. prausnitzii*). After 6 days a second sample is requested, where after the intervention with riboflavin can commence. These two samples prior to the riboflavin intervention are meant to give a reflection of the amount of *F. prausnitzii* without stimulation and the mean individual degree of fluctuation (control period). During the riboflavin intervention period, the participant is asked to take one capsule of riboflavin (100 mg) per day. After ten days, and on the final day of taking the supplement another stool sample will be requested (see check lists). This to measure the effect of riboflavin on the amount of *F. prausnitzii*. On the second clinical visit patients will be asked to bring the riboflavin container. The capsules will be counted as a control to assess if the patient has followed the dosing instructions. The riboflavin supplement is then stopped, and another stool sample will be requested two weeks after stopping. Furthermore, the changes in bacterial composition, and bacterial products (i.e. butyrate) before and after the riboflavin intervention will be assessed. The stool samples will be tested on *F. prausnitzii* and other (butyrate producing) bacteria, using fluorescent in situ hybridization (FISH) with specific probes. On two days (day 6 and day 28, see checklist) patients will be asked to divide de faeces over two containers instead of one. This extra container on these days contains a glycerol (20%), cysteine and pbs buffer (10 ml). This is used to preserve the bacteria for

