## **7.4 Summary of known and potential risks and benefits**

#### Riboflavin

No adverse effects associated with riboflavin consumption from food or supplements have been reported. In a study by Schoenen and coworkers (1994) no short-term side effects were reported in 49 patients treated with 400 mg/day of riboflavin taken with meals for at least 3 months. The lack of harm resulting from high oral doses of riboflavin may be due to its limited solubility and limited capacity for absorption in the human gastrointestinal tract (Levy and Jusko, 1966; Stripp, 1965; Zempleni et al., 1996) and its rapid excretion in the urine (McCormick, 1994). Zempleni et al. (1996) showed that the maximal amount of riboflavin that was absorbed from a single oral dose was 27 mg. Similarly in a study by Stripp (1965) there was limited absorption of 50 to 500 mg of riboflavin with no adverse effects.

Based on the studies above as well as the widespread market presence of 200 mg riboflavin supplements without reported adverse effects, the (US) Council for Responsible Nutrition (CRN) published an opinion in 2013, setting a tolerable upper intake level (UL) of 200 mg/d riboflavin

Furthermore, the above (section 7.3) described finding of an increase in the number of *F. prausnitzii* and butyrate after riboflavin intake in healthy volunteers is promising. A similar (or even larger increase) in the number of *F. prausnitzii* (and butyrate) in the bowel of Crohn's disease patients by means of a simple supplement may result in the improvement of health of Crohn's disease patients. No adverse effects are known of this supplement, however vitamin B2 can cause a temporary and harmless bright yellow discoloration of the urine.

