## 8.3 Study procedures

Standard faeces samples (five time points: day 0, day 6, day 17, day 28 and day 42) will be divided into three fractions:

- The first fraction (0.5 gram) will be fixed with 4% paraformaldehyde in Phosphate Buffered Saline (PBS) and used for FISH analysis with specific probes. (29)
- The second fraction (100 µgram) will be used for the analysis of volatile fatty acids.
- The third fraction (0.5 gram) will be stored for microbiome analysis by Next Generation Sequencing (microbiome analysis, by 16S RNA sequencing and MiSeq Illumina).
- The remainder is retained for dry weight determination, pH analysis and lactate analysis.

Faeces samples on glycerol, cysteine and PBS mix (two time points: day 6 en day 28):

-These samples will be used for the electrical current measurements of faeces and cell culturing experiments.

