#### **Measurement of electrical current and cell culturing experiments**

The experiments of the current measurements will take place conform the methods of Khan et al. A two-chambered microbial fuel cell will be used. The current before and after the riboflavin intervention will be measured. (16) In addition a small fraction of this sample will be used for cell culturing experiments.

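### Secondary objective 6 credits a rise in faecal current to more electron-shuttling bacteria, but the day-6 versus day-28 contrast, as written, cannot separate more bacteria from more riboflavin.

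*Combined protocol and SAP*

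**What the plan says.** Objective 6, in the Summary and in Section 2, links two things, asking "whether riboflavin intervention leads to an increase in electrical current in the faeces, as a result of an increase in extracellular electron shuttling bacteria". The rationale in Section 1 gives the same explanation and reports, from a cited laboratory study, that "riboflavin is required for the extracellular shuttling of electrons by" *F. prausnitzii*.

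The material for the current assay is listed in Section 8.3: "Faeces samples on glycerol, cysteine and PBS mix (two time points: day 6 en day 28". On timing, Section 3 says "After ten days, and on the final day of taking the supplement another stool sample will be requested", and note 4 to Table 1 also places the week-3 measurements on the last day of supplementation. A further stool sample is taken on day 42, after two weeks off the supplement, but it is not used for current.

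Section 8.3 describes the assay briefly: a microbial fuel cell run by a cited method. It adds that "The current before and after the riboflavin intervention will be measured". It mentions no measurement of faecal riboflavin and no step that brings the two samples to a common riboflavin level. Section 10.2 lists current among the before-and-after parameters. Section 10 names no test for it and does not relate it to bacterial counts. Section 8.2 states that participants are not randomised and serve as their own controls.

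**The concern.** The objective is about bacterial number, but the measured quantity is current. Current can depend both on how many shuttling bacteria are present and on how much riboflavin is available to carry their electrons. The intervention supplies riboflavin. A rise between day 6 and day 28 could therefore come from more bacteria, from more mediator acting on the same bacteria, or from both.

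At stake is whether a positive result on objective 6 may be read as evidence for the proposed mechanism. There is no concurrent control group to help, and added mediator would be expected to move the result towards the hypothesis.

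**Working it through.** The plan gives no expected value, variance or sample size for current. The 42 patients per group are derived for the *F. prausnitzii* count, so there is no figure to reproduce for this endpoint. The check has three parts.

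**1. Is day 28 on treatment?** Section 7.7 gives 21 days of one capsule per day (23 capsules, 2 of them spare). If day 28 is the 21st capsule day:

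- first capsule day = 28 - 20 = day 8
- treatment day on day 17 = 17 - 8 + 1 = 10, which matches the ten-day sample in Section 3
- day 42 - day 28 = 14 days, which matches the sample two weeks after stopping

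The calendar is consistent. Day 6 is before supplementation and day 28 is on it.

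**2. Could riboflavin differ between the two samples?** The daily dose is 100 mg (Section 7.5). Section 7.4 reports that "the maximal amount of riboflavin that was absorbed from a single oral dose was 27 mg".

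- unabsorbed amount ≥ 100 - 27 = 73 mg per dose

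This assumes that the 27 mg limit applies to these patients taking the capsule at breakfast. Section 7.1 says food raises absorption, and Section 7.4 does not say whether the 27 mg was measured with food. The documents do not say how much of the remainder survives to the stool, how far the 10 ml of buffer in the tube dilutes it, or how current responds to it. The trial's premise does require riboflavin to reach the gut bacteria.

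**3. What does the contrast estimate?** Write current as f(N, R), where N is the number of shuttling bacteria and R the riboflavin available in the cell. The planned contrast is

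f(N28, R28) - f(N6, R6) = [f(N28, R28) - f(N6, R28)] + [f(N6, R28) - f(N6, R6)].

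The first bracket is the bacterial effect that objective 6 asserts. The second is the mediator effect with bacteria unchanged. The plan yields one difference and cannot divide it between the two.

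If both samples are run at a common level R\*, the contrast becomes f(N28, R\*) - f(N6, R\*) and the second bracket disappears. Running day-6 material with and without added riboflavin gives f(N6, R\*) - f(N6, R6). If current does not fall as riboflavin rises and R\* is saturating, this is at least as large as the second bracket, so it bounds the mediator effect. If it is near zero, mediator supply was not limiting on day 6 and the concern disappears.

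**The case against.** The strongest reply is that the assay is taken from a cited method, which may wash the cells or fix the riboflavin concentration. In that case the two samples are already comparable. This stands as a limit on the point: the method cannot be seen here. A reader might infer that the day-28 sample certainly carries extra mediator into the fuel cell. The documents do not support that; they show only that equalisation is not stated.

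The second reply is that the trial counts bacteria directly. FISH for *F. prausnitzii* and for total bacteria, and sequencing, are planned on the same day-6 and day-28 stools. A reader might infer that an unchanged flora would be reported as an increase in bacteria. That goes too far, because a flat *F. prausnitzii* count beside a raised current would be visible in the trial's own data. What remains is narrower. No analysis links current to counts, FISH does not cover shuttling bacteria as a class, and if counts and current rise together the share due to mediator is still unknown.

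Third, the size is unknown. Turning the 73 mg into a concentration per gram of stool needs a stool mass and a survival fraction that the documents do not give, and there is no dose-response for current. That stands: an upward bias is the expected direction, possible but not shown.

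Finally, two remedies that come to mind are weak. Washing both samples free of riboflavin may remove the mediator that the reaction needs, and it handles an organism that Section 1 describes as extremely oxygen-sensitive. A current sample on day 42 would not separate the causes, since both bacteria and mediator may have reverted by then.

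**Conclusion.** The point holds in limited form. As written, the before-and-after contrast in current cannot support the causal part of objective 6, because the on-treatment sample may differ from baseline in mediator as well as in bacteria. This rests on three things in the documents: the causal wording, riboflavin's stated role in the shuttling, and current being sampled only off supplement (day 6) and on its last day (day 28). It also assumes that the cited method does not already equalise riboflavin.

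The only size the documents allow is at least 73 mg of unabsorbed riboflavin per dose, and that carries the absorption assumption noted above. The effect on current cannot be quantified, and it may be nil if riboflavin is not limiting on day 6. A reader might conclude that objective 6 is unanswerable or that the trial's main result is compromised. Neither follows. A simple laboratory control makes the objective much more informative, and the primary analysis of *F. prausnitzii* counts and its sample size do not depend on current. This is a minor-to-moderate point on one secondary objective, and a cheap improvement.

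**What to change.** In Section 8.3, state how riboflavin is handled in the fuel cell. If the cited method already equalises it, one sentence saying so settles this part. If not:

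- Run the day-6 and day-28 samples at the same saturating riboflavin concentration.
- Where material allows, also run the day-6 sample with and without added riboflavin, to size the mediator effect.

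In either case, in Section 10 report the change in current alongside, or per, the same-day FISH counts of *F. prausnitzii* and total bacteria. This is still needed at equal riboflavin, because current could also change through activity per cell.

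If this is not done, delete the final causal clause of objective 6 in the Summary and Section 2, bring the matching sentence in Section 1 into line, and conclude only that current changed.

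The cost is a small laboratory step, slightly more of the stored sample, and a sentence or two in Sections 8.3 and 10. No visit, patient or stool collection is added. Rewording the objective costs nothing.
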